**Table 1. Outline of procedures and assessments**

	BL	Day 1	Day 8
Baseline Screening Physical Exam, Medical History, Labs, ECG, Urine Pregnancy Test, SCID, ASI, KMSK, TLFB	X		
Smoking Related Measures FTND QSU, MNWQ, Self-Report, Breath CO	X X	X	X
Stress/Anxiety Related Measures HAM-A, PSS, DASS-21, VAS	X	X	X
Sleep Related Measures PROMIS Sleep Disturbance Short Form, Epworth, PSQI Actigraphy Sleep Monitoring (Garmin Vivosmart® 3)	X	X	X
Receive 7 days of suvorexant (0 or 20 mg)		X	
Relapse Risk Assessment Stress Reactivity Assessment (HR, BP, salivary cortisol, VAS) Dual-Component Smoking Relapse Assessment		X X	X X

**SCID** - Structured Clinical Interview for DSM-5, **ASI** - Addiction Severity Index; **KMSK** - Kreek-McHugh-Schluger-Kellogg scale; **TLFB** - Timeline Followback; **FTND** – Fagerstrom Test for Nicotine Dependence; **QSU** – Questionnaire on Smoking Urges-brief; **MNWQ** – Minnesota Nicotine Withdrawal Questionnaire; **CO** – Carbon Monoxide; **HAM-A** – Hamilton Anxiety Rating Scale; **PSS** – Perceived Stress Scale; **DASS-21** – Depression Anxiety Stress Scales; **VAS** – Visual Analog Scale; **PSQI** – Pittsburgh Sleep Quality Index; **HR** – Heart Rate; **BP** – Blood Pressure

**Participant Recruitment and Setting (N = 20, n = 10/group)** will consist of otherwise healthy, cigarette smokers that report smoking at least 10 cigarettes/day, are between 18 and 65 years old and fluent in English, without greater than mild substance use disorder on drugs other than nicotine. Because suvorexant is a sedative-hypnotic contraindicated with alcohol use, participants will be excluded if they: meet DSM-5 criteria for an alcohol use disorder; report recent problem drinking (5/4 drinks for males/females in < 2.5 hours or > 10 alcoholic drinks per week); report being unwilling to stop using alcohol in the evening for the two weeks of the study; are pregnant, nursing, or planning on becoming pregnant during the course of the study; or if they have any other illness, condition, or use of medications which in the opinion of the PI and/or admitting physician would preclude safe and/or successful completion of the study. Recruitment strategies will include local advertising in print media, public service announcements on radio, and referrals to Center for Neurobehavioral Research on Addiction (CNRA) in the Houston metropolitan area. We will also recruit from the Department of Psychiatry Recruitment Registry: HSC-MS-23-0768.

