### **Measures**

**Baseline Screening** As part of the CNRA general evaluation protocol (HSC-MS-05-0322), to determine eligibility, participants will receive a comprehensive medical and psychiatric evaluation including: a medical-history questionnaire, physical examination, laboratory chemistries (e.g., blood chemistry screen, complete blood count, urinalysis and urine pregnancy test), and ECG. Clinicians will conduct the **SCID**, the **ASI**, the **KMSK** assessment of lifetime substance use interview, and **TLFB**.

**Smoking-Related Measures** Nicotine dependence will be assessed using the **FTND**. Self-report will be used to collect self-reported number of cigarettes used in the past 7 days. Nicotine craving will be assessed using a brief, 10-item version of the **Questionnaire of Smoking Urges (QSU-brief)**. Nicotine withdrawal will be assessed using the 8-item **MNWQ**. **Breath CO** will be used to measure severity of smoking and overnight smoking abstinence.

**Sleep-Related Measures** Quality of sleep in the past week will be primarily assessed using the **PROMIS Sleep Disturbance Short Form**, a well validated and reliable subjective measure of sleep quality. Secondary measures will include the **Epworth Sleepiness Scale**, and **PSQI**. Sleep actigraphy (total hours, levels, and movement) will be measured via the Garmin Vivosmart® 3 device as validated by recent research.

**Stress and Anxiety Measures** Stress and anxiety will be assessed using standard, validated questionnaires using the **HAM-A**, **PSS**, and **DASS-21**. Additionally, a single-item **VAS** measure will be used to assess self-reported stress.

**Human Laboratory Measures** Experimental measures will be conducted on study days 1 and 8. Participants will be instructed to stop smoking by 10 pm the day before, in order to ensure they meet the breath CO criterion ( $CO \leq 4$  ppm) indicating overnight abstinence. In addition to measuring nicotine craving and withdrawal using the QSU and MNWQ, respectively, we will conduct two additional assessments.

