### **Specific Analyses**

Hypothesis 1: GLMM will model each primary relapse risk outcome (craving (QSU), stress reactivity (heart rate and salivary cortisol), and latency to self-administration) as a function of the main effects and interaction between time (pre vs. post) and treatment group, including any necessary control variables (as defined above in the confounding variables section) and a random intercept for participant. Secondary measures of craving and stress reactivity will be assessed in similar fashion with Type I error correction for the frequentist analyses.

Hypothesis 2: GLMM will model each sleep metric (quality, duration, and restlessness) as a function of the main effects and interaction between time (pre vs. post) and treatment group, including control variables and a random intercept for participant. Secondary measures for sleep will be assessed in similar fashion with Type I error correction for the frequentist analyses.

Exploratory Hypothesis GLMM will model each relapse risk outcome (craving, stress reactivity, and latency to self-administration) as a function of the main effects and all higher-order interactions between time (pre vs. post), given sleep metrics (in unique models: quality, duration, and restlessness), and treatment group, including control variables and a random intercept for participant.

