### **Sample Size and Power Considerations**

Frequentist Analyses With regard to sample size, the current proposal is limited to a maximum credible sample of  $N = 20$  ( $n = 10/\text{group}$ ) that may be accrued in the given time window and the budget of the funding mechanism. While the specific analyses proposed above will be thoroughly evaluated, ultimately the research proposed here will be exploratory and hypothesis-generating for the purpose of a larger-scale trial. Given these limitations, frequentist power calculations are presented as due diligence for the current proposal (conducted via G\*Power 3.1.9.4) and focus on the broadest analytic goal presented by Hypothesis 1 (change over time for each treatment group for a given relapse risk outcome). Assuming alpha = 0.05, a maximum credible sample size  $N = 20$  (10/group) provides 80% power to detect a large effect size Cohen's  $f = 0.66$ .

Bayesian Analyses An advantage of the dual frequentist/Bayesian approach is that current proposals are able to utilize the ability of Bayesian inference to provide probabilistic estimates of effects even in the context of small sample sizes.

of lower power to detect small effect sizes. Given the exploratory nature of the present research, Bayesian analyses will focus on posterior probabilities  $\geq 0.75$  (equivalent to a Bayes factor = 0.33 or 3.0) to emphasize the value in discerning a signal for model effects across analyses.

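### Craving, and very probably PROMIS sleep quality, are measured at two pre-dose visits, but the pre/post model does not define pre or say how the screening value is used, and it makes inefficient use of the pre-dose data

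*Combined protocol and SAP*

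**What the plan says.** The Specific Analyses section gives the sleep model: "GLMM will model each sleep metric (quality, duration, and restlessness) as a function of the main effects and interaction between time (pre vs. post"). Arm is the other factor in that interaction, and the model adds control variables and a random intercept for participant. Hypothesis 1 gives the same structure to craving (QSU), heart rate, cortisol and latency. No visit is assigned to *pre* or *post*.

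Table 1 has columns BL, Day 1 and Day 8.
- The row "QSU, MNWQ, Self-Report, Breath CO" is marked at all three visits; the extra mark at BL fits the FTND line above it.
- The row starting "PROMIS Sleep Disturbance Short Form, Epworth, PSQI" shares its cell with actigraphy and shows one mark per visit.

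Medication is supplied on Day 1 and taken at 10 PM, so BL and Day 1 assessments both come before the first dose. For the laboratory days (1 and 8), "Participants will be instructed to stop smoking by 10 pm the day before". No such instruction is stated for BL.

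The Confounding Variables paragraph admits a baseline covariate only if it is related to both assigned group and outcome. The sample is given as "Participant Recruitment and Setting (N = 20, n = 10/group").

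**The concern.** A two-level time factor cannot describe three visits until someone decides what happens to BL. The text leaves that decision to the analyst, for a primary Hypothesis 1 outcome (QSU) and the main sleep-quality measure (PROMIS).

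Two things are at stake. The first is precision, which is scarce with 10 per arm: a change score throws away information that the pre-dose values hold. The second is calibration. QSU measures momentary craving, and BL has no stated abstinence while Day 1 follows a night without smoking. If both were coded *pre*, any shift between them would have no term in the model and would go into residual error.

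**Working it through.** **Inputs from the plan.** N = 20 with 10 per arm; "Assuming alpha = 0.05, a maximum credible sample size" of 20 "provides 80% power to detect a large effect size", Cohen's f = 0.66, for "change over time for each treatment group for a given relapse risk outcome".

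**Assumed, because the plan gives no values.** Outcome SD 1 at each visit, complete data, correlation r between visits, and a BL-to-Day 1 abstinence shift D that is the same in both arms.

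**Step 1: the plan's figure.** For two groups, noncentrality is 0.66² × 20 = 8.71 on (1, 18) df. Power is 0.797, and exactly 80% needs f = 0.662. So f = 0.66 reproduces as a two-group comparison of a change score standardized by its own SD, with d = 2 × 0.66 = 1.32.

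**Step 2: variance of the treatment contrast.** With two visits, complete data and a random intercept, the participant term cancels, and the group-by-time effect is the arm difference in Day 8 minus Day 1.

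| r | Change score, 2(1−r) | Day 8 adjusted for Day 1, 1−r² | Day 8 adjusted for mean of BL and Day 1, 1−2r²/(1+r) | Last vs change score | Last vs Day 1 adjustment |
|---|---|---|---|---|---|
| 0.4 | 1.20 | 0.84 | 0.77 | −36% | −8% |
| 0.6 | 0.80 | 0.64 | 0.55 | −31% | −14% |
| 0.8 | 0.40 | 0.36 | 0.29 | −28% | −20% |

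The last column is BL's own contribution.

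**Step 3: power.** The effect is set at 1.32 × √(2(1−r)), which is 1.18 SD at r = 0.6, so that the change score has about 80%. Simulated power at r = 0.6 is about 80% for the change score, 86% with Day 1 as covariate and 90% with the mean of both. Over r = 0.4 to 0.8 the adjusted figures are about 81–89% and 88–91%, lowest at r = 0.8; runs agree to about one point. Type I error stays at about 0.05.

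The 88–91% assumes equal weights for BL and Day 1. If the two weights are estimated separately, as an unstructured covariance in effect does, a check with 40,000 trials per setting gave about 86–90%. The gain over Day 1 alone was then about nil at r = 0.4, 3 points at r = 0.6 and 5 points at r = 0.8.

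**Step 4: weakly correlated BL.** Let Day 1 and Day 8 correlate 0.6, and BL correlate 0.4 with each. Day 1 alone explains 0.6² = 0.36 of the Day 8 variance. The mean of both explains 0.5²/0.7 = 0.357. Optimal weights explain (0.16 + 0.36 − 0.192)/0.84 = 0.39, but those weights must be estimated from 20 people. Simulated power:

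| BL correlation | Day 1 only | Mean of both | Both, separate weights |
|---|---|---|---|
| 0.4 | 85.4% | 85.3% | 84.7% |
| 0.3 | 85.0% | 82.7% | 83.5% |

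BL then adds nothing or costs 2 to 3 points at worst, but every entry stays above the planned 80%.

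**Step 5: pooling BL and Day 1 as *pre*.** The expected residual mean square becomes [20((1−r) + D²/2) + 18(1−r)]/38 instead of 1−r. With D = 1:
- r = 0.5: 29/38 = 0.763 against 0.5, so the standard error is √1.526 = 1.24 times too large.
- r = 0.7: 21.4/38 = 0.563 against 0.3, so it is √1.877 = 1.37 times too large.

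Simulated type I error is 0.017 and 0.008, and power 0.818 and 0.737, against about 0.80 for Day 1 alone. Bias of the treatment-by-time effect is about zero (−0.001). The time main effect moves by half the shift. With D = 0, pooled power is 0.916 and type I error 0.051.

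**The case against.** The best reply is that *pre* means Day 1 on any normal reading. Section E1 lists the visits as screening, then baseline observations, then one follow-up. The Human Laboratory Measures paragraph places QSU and MNWQ with the experimental measures on days 1 and 8. This stands. A reader might infer that the plan intends to mix BL with Day 1; no text says so, and Step 5 describes only an analysis that the wording fails to exclude. Nor would pooling always lose power: with little or no shift it beats Day 1 alone, and the loss needs a large shift and a high correlation.

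A reader might also infer that BL must be either discarded or mixed in. The documents leave other routes: the confounder screen could admit it, and section E1 uses a QSU score cut at 50 as a randomization factor. Neither is reliable. The screen requires a chance association with arm. The Confounding Variables paragraph points to Study Design, which lists only FTND, and a dichotomized QSU would do nothing for PROMIS.

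The other limits also stand:
- Most of the gain comes from baseline adjustment itself, not from BL.
- Using BL is not free at this sample size (Step 4), and weak correlation is plausible for QSU because the smoking state differs.
- The abstinence argument does not carry over to PROMIS, which covers the past week; its case rests on precision.
- The PROMIS schedule is read from a damaged row: three visits is likely, not certain.
- HAM-A, PSS and DASS-21 are named in no model in Specific Analyses. They are affected only if treated as secondary measures there. MNWQ is not named in those models either; I assume it is analysed like QSU.

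**Conclusion.** The point holds as a gap in specification and a modest loss of efficiency. For QSU, and very probably PROMIS, the plan schedules two pre-dose values and writes a model that on its natural reading is a change score from Day 1. Adjusting for pre-dose values raises power at f = 0.66 from about 80% to 81–89% (Day 1) or 88–91% (both, equally weighted), assuming equal correlations of 0.4–0.8 and complete data. BL's own share is an 8–20% variance reduction under that assumption, and nothing or a small loss if BL correlates only 0.3–0.4 with Day 8 against 0.6 for Day 1.

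A biased treatment effect or an inflated type I error should not be inferred. A shift common to both arms leaves the interaction unbiased, and pooling makes the test conservative. Heart rate, cortisol and latency are measured only on Days 1 and 8, so *pre* and *post* are clear there. The study calls itself exploratory, which limits the consequences. But its sample is capped at 20, so precision from data already scheduled is worth taking.

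**What to change.** In Specific Analyses, under Hypotheses 1 and 2:

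1. State that *pre* is Day 1 and *post* is Day 8, and that BL is never pooled with Day 1.
2. For outcomes measured at all three visits, replace the two-level time factor by a visit factor (BL, Day 1, Day 8). Constrain the arm means to be equal at BL and at Day 1, since both precede dosing, and test the arm difference at Day 8. The constraint is needed: an unconstrained Day 8 minus Day 1 contrast would not recover the information in BL.
3. Use an unstructured covariance, not a random intercept alone, so that BL is not forced to the same weight as Day 1. Use the same mean structure in the Bayesian fit.
4. State which secondary questionnaires this covers, and confirm the PROMIS visits in Table 1.

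A simpler alternative is Day 8 adjusted for Day 1, adding BL for PROMIS. It captures most of the gain and limits the risk from a weakly correlated BL value for QSU.

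The cost is a few sentences, no new data, one further visit mean and a few covariance parameters. Estimating the weights costs about 2 points of power against equal weighting when the correlations really are equal, and 0.7 to 1.5 points against Day 1 alone when BL correlates weakly.

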### **PRIMARY HYPOTHESES AND SPECIFIC AIMS**

**Specific Aim 1:** Assess the impact of suvorexant on established measures of smoking relapse risk (craving, withdrawal, stress reactivity, latency to self-administration).

**Hypothesis 1:** Participants receiving suvorexant (vs. placebo) will demonstrate lower craving, stress reactivity, and longer latency to self-administration of cigarettes in a human laboratory experiment.

**Specific Aim 2:** Validate the somnolent effect of suvorexant on sleep metrics in a sample of individuals with tobacco use disorder.

**Hypothesis 2:** Participants receiving suvorexant (vs. placebo) will demonstrate superior sleep metrics, including higher perceived sleep quality, longer duration of sleep, lower restless sleep).

**Exploratory Aim:** Examine the potential moderating effect of suvorexant on the relationship between sleep metrics and established measures of smoking relapse (noted in Aim 1).

**Exploratory Hypothesis** The relationship between superior sleep metrics (quality, duration, restlessness) and measures of smoking relapse risk (lower craving, withdrawal, stress reactivity, and latency) will be magnified in participants receiving suvorexant (vs. placebo).

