## DATA ANALYSIS PLAN

**Confounding Variables** Preliminary data analyses will inspect relationships between baseline/demographic variables, experimental group, and specified outcome variables via traditional statistical tests (e.g., chi-square, Mann-Whitney-Wilcoxon, Kruskal-Wallis, and *t*-tests). Baseline covariates that demonstrate a relationship with both assigned group and outcome variables meet criteria for being potential confounders and will be included as a covariate in any statistical models for hypothesis testing. All analyses will statistically control for the stratification variables (detailed above in the Study Design section).

**Inferential Paradigm** Following recommendations for clinical trials in the literature analyses will proceed using parallel frequentist and Bayesian statistical inference. Frequentist results yield The probability of the data (or data more extreme), given the null hypothesis, while Bayesian results yield The probability of the null hypothesis given the data and The probability of the alternative hypothesis given the data.

alternative hypothesis. If possible, Bayesian analyses will incorporate informative priors as they develop in the literature; otherwise, weakly informative priors will be incorporated as a default (e.g., for regression coefficients:  $\sim N[\mu=0, \sigma^2=100]$ ; for non-linear outcomes this prior applies to the coefficient within the link-function). Sensitivity analyses using optimistic and pessimistic, skeptical priors will evaluate prior assumptions. Assessing the convergence of Bayesian analyses on the posterior distributions via Monte-Carlo Markov chain (MCMC) will use graphical (Trace Plot, Autocorrelation Plot) and quantitative (Geweke Diagnostics, Gelman-Rubin Diagnostics, and Heidelberger-Welsh Diagnostics) evidence. Evaluation of posterior distributions will permit statements regarding the probability that effects of varying magnitudes exist, given the data. Statistical analyses will use SAS v. 9.4 and the most up-to-date stable release version of the R statistical computing environment using packages rstan and brms.

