**Statistical Modeling** Analyses will primarily use generalized linear modeling (GLM) with multilevel components (GLMM) for correlated observations. Specifically, for each hypothesis, GLMM will model each outcome measure of interest as a function of group, potential confounding variables (as described above), and random effects to account for correlated observations where necessary. Continuous, count, and dichotomous outcomes will utilize normal, Poisson/negative binomial, and binomial distribution families respectively, with identity, log, and logit link functions as appropriate. Evaluation of distributional assumptions will use residual plots, formal statistical tests, and posterior predictive checking. Violations of assumptions will be addressed via transformation, robust estimation, stratification, and/or coefficient scaling where appropriate.

**Missingness & Multiple Comparisons** While the short nature of the proposed trial should reduce the prospect of missing data, for the frequentist analyses, missing data will be addressed via maximum likelihood, explicit modeling of missingness, and/or imputation. Bayesian analyses will use joint modeling of outcomes and missingness to handle missing data. Each approach is robust to ignorable missingness (i.e. MCAR and MAR). Analyses will address non-ignorable missingness using pattern-mixture modeling. Sensitivity analyses will permit evaluation of the robustness of findings to missing data assumptions. While Bayesian analyses are not influenced by traditional concerns of multiplicity, frequentist analyses will utilize false discovery rate (FDR) to control for Type I error across multiple tests for secondary outcomes where delineated.

**Exploratory Data Analyses** Where not otherwise specified, to maximize the utility of the present data, exploratory analyses will evaluate relationships between variables captured as part of the study. For example, while not represented in specific hypotheses, changes in self-reported smoking behavior as functions of other variables in the present study will be explored.

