## **E3. Potential Risks**

**Suvorexant** (BELSOMRA) is an orexin receptor antagonist indicated for the treatment of insomnia, characterized by difficulties with sleep onset and sleep maintenance. Recommended dose is 10 mg, 1x per night taken within 30 minutes of going to bed, with at least 7 hours of planned time before awakening. If the 10 mg dose is well tolerated but not optimally effective, it can be increased but not to exceed 20 mg once daily. Medication is taken PO, with dosage in tablets of 5, 10, 15, and 20 mg. Contraindicated in patients with narcolepsy. Precautions include daytime somnolence; dose-related risk of impaired alertness and motor coordination, including impaired driving; patients taking 20 mg should be cautioned against next-day driving; nighttime “sleep-driving” and other complex behaviors while out of bed and/or not fully awake; worsening of depression or suicidal thinking; compromised respiratory function; sleep paralysis, hypnagogic/hypnopompic hallucinations. Risk of the above symptoms increases with use of CNS depressants and alcohol. In obese women (BMI > 30), there is increased risk of exposure-related adverse effects. Belsomra is a schedule-IV compound with mild/modest abuse-potential in the same class as existing sleep medications and anxiolytics. The most common adverse reactions include somnolence and slowed motor coordination. Not recommended for use in patients taking strong CYP3A inhibitors, efficacy may be reduced, or for patients with severe hepatic impairment. Based on animal data, Belsomra may cause fetal harm.

**Risks for Behavioral and Psychometric Testing.** Items on certain psychological/psychiatric questionnaires and interviews might be perceived as personally discomforting to some subjects. Similarly, subjects may experience discomfort due to withdrawal symptoms as part of the smoking relapse assessment. With regard to the actigraphy sleep monitoring, participants may experience mild discomfort while acclimating to wearing the device during sleep. While subjects may be uncomfortable reporting these issues, the risks of serious sequelae are extremely low.

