**Infection Risk Reduction Counseling and Testing.** As described in sections D1, D2, E1 and E4, we recognize these risks and have included the necessary tests and precautions for disease transmission and infection risk (HIV, tuberculosis (TB), hepatitis, syphilis). HIV counseling will be made available as deemed appropriate by medical personnel in the treatment research center.

**Safety of Research Participants Outside of the Research Site.** These issues are addressed in section E4. They are repeated here for clarity. In addition to the screening criteria for inclusion, each visit to the laboratory will include a full side effects profile. Additionally, subjects will be evaluated for signs of impairment or side effects, first by a research assistant and then by a PI and CNRA research nurse. The assessment battery includes subjective questionnaire, nystagmus, touching nose, balance, and walking a straight line. If the subject is determined to be unimpaired, s/he will be released promptly. If any signs of sedation or other impairment are detected, participants will be required to remain at the experimental site until such symptoms are no longer observed. In the event of either an unexpected adverse event or heavy sedation, we have several measures in place. First, [name] (CNRA medical director) is a licensed MD with clinical experience and training in emergency medicine. Thus, a physician will be in the immediate vicinity of laboratory. Offices and clinical space are contiguous to the lab. Second, Ben Taub Hospital, a level 5 emergency medical center is located less than 5 minutes away from our building. Finally, in the event of extended sedation or impairment in which any subject does not appear clear-headed, feeling well, and in full control of his or her behavior, two

steps will be taken. First, the subject will remain in the lab until such time that the PI, medical director, or research nurse deems that it is safe for him or her to leave (e.g., passing the test described above). Second, if necessary, we will arrange for a taxi service to drive the subject back to his/her home.

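### The Epworth measures daytime sleepiness, a named suvorexant risk, but is tested only as an FDR-corrected secondary sleep contrast, and the analysis plan names no safety comparison by arm (minor)

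*Combined protocol and SAP*

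**What the plan says.** Under Measures, sleep quality is assessed mainly by the PROMIS short form; then "Secondary measures will include the" Epworth and the PSQI. The reference cited for the Epworth describes it as a method for measuring daytime sleepiness.

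Under Specific Analyses, Hypothesis 2 is modelled with time, treatment group and their interaction, plus a random intercept. The section then adds: "Secondary measures for sleep will be assessed in similar fashion with Type I error correction for the frequentist analyses". The Missingness & Multiple Comparisons paragraph names the correction: "frequentist analyses will utilize false discovery rate (FDR) to control for Type I error across multiple tests for secondary outcomes where delineated". It leaves the Bayesian analyses uncorrected. It states neither the FDR procedure nor the size of the family.

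Section E3 says of suvorexant: "Precautions include daytime somnolence; dose-related risk of impaired alertness and motor coordination, including impaired driving". It also lists somnolence among the most common adverse reactions. All active participants take 20 mg, the highest approved dose.

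The data analysis plan mentions no adverse events, impairment tests or tolerability comparison between arms. Two general provisions come near. Under Inferential Paradigm: "Evaluation of posterior distributions will permit statements regarding the probability that effects of varying magnitudes exist, given the data". Under Exploratory Data Analyses: "exploratory analyses will evaluate relationships between variables captured as part of the study".

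**The concern.** Multiplicity correction guards against false claims of benefit. Applied to a known harm, it makes that harm harder to flag. This pilot is meant to inform a larger trial, which will need an estimate of next-day sleepiness with an interval. With 10 per arm, a corrected non-significant test says little, and a reader could take it as reassurance. The planned contrast also gives a wider interval than the same data allow.

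**Working it through.** **Inputs from the documents.** N = 20, 10 per arm; alpha 0.05; f = 0.66 for 80% power (Sample Size and Power Considerations, given for Hypothesis 1); two named secondary sleep scales.

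**Assumptions.** Two-sided tests; complete data; Benjamini-Hochberg at 0.05 over the two named scales; f = 0.40 as a smaller effect; Day 1 to Day 8 correlation r of 0.3, 0.5 or 0.7. The documents give no Epworth SD or expected effect.

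**1. The plan's own figure.** Noncentral F with (1, 18) df and noncentrality f² × N = 0.66² × 20 = 8.71 gives power 0.797. The stated 80% reproduces as a plain two-group comparison.

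**2. Uncorrected power for the planned contrast.** With two time points, a random intercept and complete data, the arm-by-time contrast is the difference in mean change. Setting f on the change score gives d = 2f, and a noncentral t with 18 df gives:
- f = 0.40 (d = 0.80): 39.5%
- f = 0.66 (d = 1.32): 79.7%

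**3. Cost of FDR.** With two tests, Benjamini-Hochberg rejects for the Epworth if its p ≤ 0.025, or if both p-values are ≤ 0.05. The level 0.025 alone gives 28.2% and 69.2%, which are floors. Simulated power:

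| | Uncorrected | PSQI unmoved | PSQI moves equally | Loss |
|---|---|---|---|---|
| f = 0.40 | 40% | 29% | 33% | 6–11 points |
| f = 0.66 | 80% | 70% | 77–78% | 2–10 points |

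If the family held five measures (assumed), power would be 18–27% at d = 0.80 and 55–65% at d = 1.32.

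**4. Choice of contrast, a separate matter.** In raw SD units, with SD known and no chance Day 1 imbalance, the 95% half-widths are:
- Change contrast: t(0.975, 18) × √(2/10) × √(2(1 − r)) = 0.940 × √(2(1 − r)) = 1.11 / 0.94 / 0.73
- Day 8 adjusted for Day 1: t(0.975, 17) × √(2/10) × √(1 − r²) = 0.90 / 0.82 / 0.67

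Simulation with estimated SD and chance Day 1 imbalance gives means of 1.10 / 0.93 / 0.72 against 0.91 / 0.83 / 0.68. At r = 0.5, adding one to three stratification covariates widens the adjusted closed-form half-width from 0.817 to 0.821–0.831, under 2%.

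**5. Power for one fixed raw effect.** The raw effect must be held constant across r. If f is fixed on the change score, the raw effect 2f√(2(1 − r)) shrinks from 0.95 to 0.80 to 0.62 SD at f = 0.40, and power seems to fall as correlation rises. At a fixed 0.80 SD, both analyses uncorrected:

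| r | Change contrast | Day 8 adjusted for Day 1 |
|---|---|---|
| 0.3 | 30% | about 41% |
| 0.5 | 40% | about 47% |
| 0.7 | 59% | about 63% |

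The simulated (right-hand) column varies by about a point between runs. At r = 0.5, where 0.80 SD equals f = 0.40, the sequence is 29–33% with FDR, 40% without it and about 47% with adjustment as well.

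**6. Frequentist and Bayesian disagreement.** Reading the 0.75 posterior rule as directional with a near-flat prior (assumed), at f = 0.40 the Bayesian analysis flags a rise that the frequentist test misses in 47% of trials without FDR and 53–58% with it. Most of this comes from N = 20 and the 0.75 threshold.

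**7. Adverse-event counts.** Fisher's exact test with 10 per arm has power 9.3% for an assumed 30% against 5%, and 23.8% for 40% against 5%. Only a descriptive listing is worthwhile.

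**The case against.** The strongest reply is that little depends on this p-value. FDR alters neither the estimate nor its ordinary interval, the Bayesian analysis is uncorrected, and the plan calls itself exploratory and offers its frequentist power as due diligence. All of that stands, and it keeps the point minor.

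A second reply is that baseline adjustment has nothing to do with FDR or safety and would help every pre/post outcome equally. That also stands, so its gain is shown separately above.

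A reader might infer that the plan overlooks harm. The documents do not support that. They provide an adverse-event log, impairment testing and a monitoring committee, and E10 says "each visit to the laboratory will include a full side effects profile". These serve individual management and oversight reports, however, and none specifies a comparison by arm. The exploratory clause would permit one but names none.

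A reader might also infer that a rise in daytime sleepiness could be counted as success, because Aim 2 is to "Validate the somnolent effect of suvorexant on sleep metrics in a sample of individuals with tobacco use disorder". The documents point the other way. Hypothesis 2 predicts superior sleep metrics and lists quality, duration and restlessness. The Background treats daytime sleepiness as a feature of poor sleep, and E3 lists it as a precaution. A rise is already implied to be unfavourable.

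**Conclusion.** The point holds as a minor one. The only planned frequentist test of a foreseeable harm is an FDR-corrected secondary contrast, and the analysis plan commits to no safety comparison by arm. FDR alone costs 6–11 points of power at f = 0.40 and 2–10 at f = 0.66. This rests on Benjamini-Hochberg over two scales; a larger family would cost more. The wider interval is a separate loss of precision: clear at r = 0.3 (1.10 against 0.91 SD), small at r = 0.7 (0.72 against 0.68 SD). Neither change cures the small sample: for a 0.80 SD rise, power after both is about 41–63% across the assumed correlations.

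**What to change.** Under Specific Analyses, Hypothesis 2, add that the Epworth is also a tolerability outcome, reported outside the FDR family. Give the Day 8 between-arm difference adjusted for Day 1, an unadjusted 95% interval and the posterior probability of an increase. State that any claim of benefit from a fall remains in the corrected secondary sleep family, so the PSQI and Epworth are still corrected together for that purpose. Optionally, list adverse-event counts by arm without formal tests.

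The cost is a few sentences; no new data, visits or participants are needed. There are two downsides: a 5% two-sided chance of a false signal on one tolerability measure, and an Epworth model that differs from those of the other sleep measures unless baseline adjustment is adopted for them too.
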